4.3. Current Therapies and Unmet Medical Need

In some countries, SPINRAZA[®] (nusinersen) is approved for the treatment of pediatric and adult patients with SMA, EVRYSDI[™] (risdiplam) is approved for the treatment of pediatric and adult patients ≥ 2 months of age with SMA, and ZOLGENSMA[®] (onasemnogene abeparvovec-xioi) is approved for the treatment of pediatric patients less than 2 years of age with SMA with bi-allelic mutations in the *SMN1* gene. Nusinersen is an *SMN2*-directed antisense oligonucleotide and risdiplam is an *SMN2*-directed ribonucleic acid splicing modifier that are designed to treat SMA caused by mutations that lead to SMN protein deficiency. Onasemnogene abeparvovec-xioi is a recombinant adeno-associated virus vector 9-based gene therapy designed to deliver a copy of the gene encoding the human SMN protein. There are currently no approved muscle-directed therapies for the treatment of SMA. Additional medical care is supportive and focuses on respiratory support, nutritional support, and management of resulting musculotendinous

contractures and neuromuscular scoliosis through bracing, physical therapy, and surgery (Wang 2007).

SMN upregulator therapies (also referred to as SMN corrector therapies), such as nusinersen, onasemnogene abeparvovec-xioi, and other products in development (e.g., small molecule SMN upregulators) act primarily upon motor neurons to prevent further loss. While approved treatments have shown improvement in motor function in younger patients with SMA, they do not act directly on the muscle to primarily address already-existing atrophy and motor functional impairment in patients with symptomatic SMA. Consequently, there remains an unmet need for an effective muscle-directed therapy that can address muscle atrophy and motor functional impairment in patients with SMA.

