4.7. Dose Rationale

Based upon data from SRK-015-001, the first in-human study in healthy volunteers, multiple doses of up to 30 mg/kg were generally safe and well tolerated. PK results from the Phase 1 SAD study suggest that SRK-015 has a profile generally consistent with that observed of mAbs, including dose-proportionality and a low coefficient of variation. The serum half-life was 23 to 33 days across the SRK-015 dose groups. The findings support the investigation of a once every 4-week dosing regimen in this Phase 2 study.

PD results suggest that SRK-015 treatment leads to robust increases in latent myostatin concentrations in the serum above baseline and demonstrate successful target engagement in humans. Moreover, the levels of target engagement attain a plateau, suggesting that the target has been saturated even with a single treatment of SRK-015 at doses of 3 mg/kg or greater. This level of PD marker appears to be sustained for approximately 84 days following a single 20 mg/kg dose, suggesting that the PD effect is durable.

The 20 mg/kg high-dose arm is aimed at attaining target saturation rapidly (e.g., within several weeks after the first dose) and sustaining that saturation with chronic administration. Based upon PK data from the Phase 1 SAD study, the drug exposure from monthly IV administrations of SRK-015 at 20 mg/kg is predicted to be substantially less than that attained in the nonclinical toxicity studies to date. For further detail on the Phase 1 PK and PD results, please refer to the SRK-015 Investigator's Brochure.

Dose exploration will be conducted in this study by including a low-dose arm of 2 mg/kg. At this dose level, it is anticipated that target saturation will not be attained upon the first dose and thus would require additional dosing. By characterizing the time course of clinical effect from this low-dose arm and comparing it with that observed from the 20 mg/kg level, the relationship between drug exposure and therapeutic effect over time can be interrogated. Insights into the level of drug exposure necessary to initiate improvements in motor function will also be attained. Together, results from this analysis will inform the dosing regimen for future clinical studies of SRK-015 in SMA.

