6.2. Treatment Assignment

Eligible patients in Cohorts 1 and 2 will receive high-dose (20 mg/kg) SRK-015. Patients in Cohort 3 will be randomized 1:1 to low- (2 mg/kg) or high-dose (20 mg/kg) SRK-015 without stratification for the duration of the Treatment Period. Based on the results of the prespecified 6-month safety and efficacy interim analyses (data cutoff date of 20 August 2020), any Cohort 3 patients who were randomized to receive low-dose (2 mg/kg) SRK-015 will be re-assigned to receive high-dose (20 mg/kg) SRK-015 after completion of the Treatment Period. The preliminary results of the 12-month analysis (database lock date of 19 January 2021) continue to support the dose change. For further detail on the Phase 2 safety and efficacy analyses results please refer to the SRK-015 Investigator's Brochure. Due to the variability in timing of regulatory authority and/or Institutional Review Board (IRB)/Independent Ethics Committee (IEC) approvals, the timepoint at which patients who received the low dose (2 mg/kg) will begin receiving the high dose (20 mg/kg) during Extension Period A will vary.

Figure 1: Study Schematic: Treatment Period

[figure not shown]

Figure 2: Study Schematic: Extension Period A

[figure not shown]

Figure 3: Study Schematic: Extension Period B

[figure not shown]

Figure 4: Study Schematic: Extension Period C

[figure not shown]

Table 2: Study Schedule of Assessments: Treatment Period

Activity/Assessment	Screening	Treatment Period																Follow-up			
		Visit Time Point (Study Day ^a)	-28 to -1	V1 0	V2 14	V3 28	V4 56	V5 84	V6 112	V7 140	V8 168	V9 196	V10 224	V11 252	V12 280	V13 308	V14 336	V15 364	UNS	V16 392	V17 448/EOS/ ET
Informed Consent	X																				
Demographics & Medical History ^c	X																				
Inclusion/Exclusion	X																				
Pregnancy Test ^d	X	X			X				X					X						X	
Weight ^e	X	X		X	X	X	X	X	X	X	X	X	X	X	X	X	X	X	X	X	
Height ^f	X	X			X		X		X		X		X			X	X	X	X	X	
Physical Examination ^g	X	X	X	X	X	X	X	X	X	X	X	X	X	X	X	X	X	X	X	X	
Vital Signs ^h	X	X	X	X	X	X	X	X	X	X	X	X	X	X	X	X	X	X	X	X	
Clinical Safety Labs ⁱ	X	X	X	X	X		X		X		X		X		X		X	X	X	X	
12-lead ECG ^j	X	X		X			X				X				X		X	X	X	X	
PK and PD Sampling ^k		X	X	X	X	X	X	X	X	X	X	X	X	X	X		X	X	X	X	
Antidrug Antibody Sampling ^l		X		X	X	X	X	X	X	X	X	X	X	X	X		X	X	X	X	
Randomization ^m		X																			
Study Drug Administration		X		X	X	X	X	X	X	X	X	X	X	X	X						
Motor Function Outcome Measures ^{b,f,n}	X	X			X		X		X		X		X				X	X	X	X	

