3.3.4 Demographic and Baseline Characteristics

The following demographic and baseline characteristics will be summarized:

- Age at Informed Consent (years),
- Age at Diagnosis (years)
- Sex,
- Race,
- Ethnicity,
- SMA History (including SMA type, contractures, and scoliosis),
- Number of Maintenance Doses Received,
- SMN2 Gene Copy Number,
- Height (cm),
- Weight (kg), and
- Body Mass Index (kg/m²)

Demographic and baseline characteristics will be summarized with descriptive statistics or counts and percentages of patients as appropriate by treatment within each cohort and in total for the ITT, Safety (if different from ITT), and PP populations.

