3.4.3 Cohort 3: Low Dose and High Dose

3.4.3.1 Primary Efficacy Analyses

The primary efficacy endpoint is the change from Baseline to Day 364 (V15) in HFMSE total score in the high-dose arm. This analysis will also be performed to evaluate the low-dose arm as well as the entire Cohort 3 in total (i.e., high-dose arm and low-dose arm pooled together).

The difference in the change from Baseline in HFMSE total score will also be explored using descriptive statistics and the corresponding 95% CI based on the Student's t-distribution will be reported.

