3.4.3.2 Secondary efficacy analyses

The following secondary endpoints will be analyzed for Cohort 3:

- Change from Baseline in the HFMSE total score at prespecified timepoints
- Proportion of patients achieving various magnitudes of change in HFMSE score from Baseline to V15 (Day 364), V8 (Day 168) and all other scheduled visits
- Change from Baseline in the RULM total score to V15 (Day 364), V8 (Day 168) and all other scheduled visits
- Proportion of patients achieving various magnitudes of change in RULM from Baseline to V15 (Day 364), V8 (Day 168) and all other scheduled visits

- Change from Baseline in the number of WHO motor development milestones attained to V15 (Day 364), V8 (Day 168) and all other scheduled visits
- Proportion of patients who attain a new WHO motor development milestone relative to baseline at V15 (Day 364), V8 (Day 168) and all other scheduled visits.

The same analysis method as the primary efficacy analysis in Cohort 3 will be used for RULM. The same analysis method as the secondary efficacy analysis in Cohort 1 will be used for the rest of variables.

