6 CHANGES FROM PROTOCOL-SPECIFIED STATISTICAL ANALYSES

The statistical analysis section was updated in protocol version 3.0, dated 21 November 2019, and protocol version 4.0, dated 13 November 2020. Subsequent changes in the statistics of the study are detailed here.

The protocol (Section 11.2.1) states, “Vital signs and laboratory outcomes will be evaluated using paired t-tests within cohorts and unpaired t-tests between the 2 dose groups for Cohort 3; corresponding two-sided 95% CIs will be computed as well for the paired and unpaired differences”. In this SAP, descriptive statistics will be used to summarize safety assessments and no statistical testing will be conducted.

The protocol (Section 11.2.2) states, “...proportion and the 95% CI based on Wilson’s method will be reported”. In this SAP, only the proportion will be reported and the 95% CI for proportion will not be calculated.

The protocol (Section 11.2.2) states, “The primary endpoints and other efficacy continuous endpoints will be analyzed using paired t-tests within cohorts and unpaired t-tests between the 2 dose groups for Cohort 3; corresponding 2-sided 95%. CIs will be computed as well for the paired and unpaired differences.” Additionally, the protocol states, “Time to outcome improvement will be assessed using Kaplan-Meier lifetables and a log rank test to compare time to efficacy for Cohort 3 low versus high dose.” In this SAP, descriptive statistics will be used to summarize efficacy and no statistical testing will be conducted.

The protocol (Section 11.4.2) states, “Safety data at all visits and efficacy endpoints at Day 168 (Visit 8) will be included in this analysis.” Due to data cleaning, efforts were focused on up to V10 (Day 224), the interim analysis will include safety data up to V10 (Day 224).

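### Does the Cohort 3 dose comparison need a covariate-adjusted estimate beside the unadjusted one?

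*Combined protocol and SAP*

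**What the plan says.** Protocol 6.2 sets the allocation: "Patients in Cohort 3 will be randomized 1:1 to low- (2 mg/kg) or high-dose (20 mg/kg) SRK-015 without stratification". Cohorts 1 and 2 are assigned directly to the high dose, so this is the only randomised contrast in the study. SAP Table 2 (protocol Table 9) takes 10 patients per group.

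In SAP 3.4.3.1 the primary analysis for Cohort 3 is the change in HFMSE at Day 364 within the high-dose arm; the low-dose arm and the pooled cohort are analysed in the same way. The contrast comes after that: "The difference in the change from Baseline in HFMSE total score will also be explored using descriptive statistics", with a t-based 95% CI. The sentence does not itself say that the difference is between doses, but the section heading and Table 2 make this clear. SAP 3.4.3.2 extends the method: "The same analysis method as the primary efficacy analysis in Cohort 3 will be used for RULM".

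No covariate model appears in SAP 3.4.3 or protocol 11.2.2. MMRM and LSMEANS occur only in the SAP abbreviation list. SAP 6 shows that this is intended: "In this SAP, descriptive statistics will be used to summarize efficacy and no statistical testing will be conducted". SAP 3.1.5 likewise rules out formal testing. On baseline data, SAP 3.3.4 says: "Demographic and baseline characteristics will be summarized with descriptive statistics or counts and percentages of patients as appropriate by treatment within each cohort".

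**The concern.** Ten per arm without stratification leaves real room for chance imbalance. If a factor that predicts the change in HFMSE is uneven between doses, the observed difference moves with it. Age is a natural candidate: Cohort 3 enters from age 2, and protocol 4.3 remarks that "approved treatments have shown improvement in motor function in younger patients with SMA". The baseline table would reveal an age imbalance, but no planned analysis shows how far the dose difference depends on it.

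The contrast also appears to matter. Protocol 4.7 says of the dose comparison that "results from this analysis will inform the dosing regimen for future clinical studies of SRK-015 in SMA", and it lists greater HFMSE improvement in the high-dose arm among the interim results behind the later dose change. If an age imbalance produced part of that difference, readers planning further studies could be misled. An ANCOVA estimate beside the unadjusted one would seem a cheap safeguard.

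**Working it through.** **Inputs.** From SAP 2.2.3: 10 per arm, SD of HFMSE change 2.5, two-sided 5%. The correlation r between a baseline factor and the change is not in the documents; it is assumed here to be 0.2 to 0.5.

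**The plan's own figure.** A two-sample t-test with 18 df, 10 per arm and standardised difference 1.325 has power 0.800, as SAP Table 2 states.

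**Planned precision.** Half-width = t(0.975; 18) × 2.5 × √(2/10) = 2.101 × 1.118 = 2.35 HFMSE points.

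**How likely is an imbalance?** The standardised imbalance in one factor has SD √(2/10) = 0.447. The probability that it exceeds 0.5 SD in either direction is 26%, 0.75 SD 9%, and 1 SD 2.5%.

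**How far does it move the estimate?** Shift = r × 2.5 × imbalance. At 0.5 SD this is 0.25 points (r = 0.2) to 0.62 points (r = 0.5), or 11% to 27% of the half-width. At 1 SD it is 0.50 to 1.25 points.

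**What happens to the planned interval?** Simulated coverage of the unadjusted 95% CI with the imbalance held fixed (40,000 trials per cell):

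| Imbalance | r = 0.2 | r = 0.3 | r = 0.4 | r = 0.5 |
|---|---|---|---|---|
| 0.5 SD | 94.8% | 94.7% | 94.5% | 94.2% |
| 1 SD | 93.4% | 91.3% | 88.4% | 84.6% |

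ANCOVA on the right covariate keeps 95% throughout. A material loss therefore needs both a rare imbalance and a fairly strong predictor.

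**What would adjustment cost?** Averaged over all imbalances, one covariate multiplies the variance by (1 − r²) × 17/16 and leaves 17 df. Break-even on variance is r = √(1 − 16/17) = 0.24. Allowing also for the larger t quantile (2.110 against 2.101), it is r = √(1 − (16/17) × (2.101/2.110)²) = 0.26. Below that the interval widens, by about 3% at r = 0.

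With the imbalance fixed at d, the width ratio is approximately (2.110/2.101) × √[(1 − r²)(1 + 5d²/16)]. At d = 1 this gives 1.13, 1.10, 1.05 and 1.00 for r = 0.2, 0.3, 0.4 and 0.5. So where adjustment would repair coverage, it does so with an interval about 13%, 10% and 5% wider at the first three values, and no narrower in any useful degree at the last.

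**Baseline HFMSE as covariate.** With equal variances at baseline and Day 364, |r| = 2.5/(2 × baseline SD). Assumed baseline SDs of 8 to 12 give |r| = 0.16 to 0.10, below break-even. The interval widens by 2–3%, and a 0.5 SD imbalance is worth only 0.20 to 0.13 points.

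**Baseline HFMSE plus age.** Taking r = 0.125 for baseline and a correlation of 0.5 between the two covariates, the mean interval width changes by +5%, +2%, −2% and −9% for age r = 0.2, 0.3, 0.4 and 0.5. A gain requires an age correlation of about 0.4 or more.

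**The case for a change.** The best case for an adjusted estimate is that it costs little and answers a question readers will ask. With two independent factors, the chance that at least one is out of balance by more than 0.5 SD is 46%. The sponsor does use the dose comparison, and two small models on data already collected would show whether the result is sensitive. The facts behind this are correct: no adjusted estimate is planned, and conditional coverage can fall below 95%.

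Most of the argument loses its force on a closer reading of the documents.

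- The protocol 4.7 sentence on future dosing follows a description of the time course of effect and of exposure over time. Time to effect has its own Kaplan-Meier analysis in SAP 3.4.3.3, and a Day 364 ANCOVA adds nothing to it.
- The dose change rested on the 6-month interim, including the absence of safety signals. A Day 364 model does not bear on that result.
- Protocol 4.3 describes what approved therapies achieved in younger patients. It does not show that age predicts 12-month change among patients who have been on stable background therapy for at least 6 months. The age-5 boundary separates Cohort 3 from Cohort 2: everyone in Cohort 3 started treatment before 5, so it shows no heterogeneity within the cohort.
- SAP 3.3.4 also lists SMN2 copy number, age at diagnosis, maintenance doses, contractures and scoliosis. Nothing in the documents ranks age above these, and with about 20 patients one or two older ones can drive a linear age term.
- Protocol 6.2 reports that "The preliminary results of the 12-month analysis (database lock date of 19 January 2021) continue to support the dose change". A covariate chosen now could not be presented as prespecified.

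What stands is that an investigator may reasonably like to see such an estimate. That is a preference about supplementary output.

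**Conclusion.** The plan is sound on this point. A simple difference with a t interval is a valid analysis of an unstratified 1:1 randomisation, and the SAP presents the contrast as exploratory, secondary to the high-dose arm's own change. Baseline characteristics are tabulated by treatment within cohort, and SAP 7 provides patient listings, so an imbalance or an influential patient can be seen directly.

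At a 0.5 SD imbalance the possible shift is 0.25 to 0.62 points against a half-width of 2.35, and coverage remains 94–95%. The worst figures, 88% and 85%, combine an imbalance with a 2.5% chance of being exceeded and an assumed correlation of 0.4 or 0.5. Adjustment for baseline HFMSE alone would probably widen the interval slightly; adding age helps only if its correlation with change is about 0.4 or more. These sizes rest on the plan's SD of 2.5, normal outcomes, 10 patients per arm, and correlations and baseline SDs that are assumptions. Since the documents supply none of those correlations, they show no assured gain, and no change to the plan is called for.

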3.4.3.2 Secondary efficacy analyses

The following secondary endpoints will be analyzed for Cohort 3:

- Change from Baseline in the HFMSE total score at prespecified timepoints
- Proportion of patients achieving various magnitudes of change in HFMSE score from Baseline to V15 (Day 364), V8 (Day 168) and all other scheduled visits
- Change from Baseline in the RULM total score to V15 (Day 364), V8 (Day 168) and all other scheduled visits
- Proportion of patients achieving various magnitudes of change in RULM from Baseline to V15 (Day 364), V8 (Day 168) and all other scheduled visits

- Change from Baseline in the number of WHO motor development milestones attained to V15 (Day 364), V8 (Day 168) and all other scheduled visits
- Proportion of patients who attain a new WHO motor development milestone relative to baseline at V15 (Day 364), V8 (Day 168) and all other scheduled visits.

The same analysis method as the primary efficacy analysis in Cohort 3 will be used for RULM. The same analysis method as the secondary efficacy analysis in Cohort 1 will be used for the rest of variables.

3.4.3.3 Tertiary Efficacy Analyses

The following tertiary endpoints will be analyzed for Cohort 3:

- Change from Baseline in Time to limitation on ESNHPT or ESBBT to V15 (Day 364), V8 (Day 168) and all other scheduled visits
- Change from Baseline in PEDI-CAT to V15 (Day 364), V8 (Day 168) and all other scheduled visits
- Change from Baseline in PROMIS Fatigue Questionnaire to V15 (Day 364), V8 (Day 168) and all other scheduled visits and
- Time to therapeutic effect as compared between low and high dose SRK-015 arms to V15 (Day 364), V8 (Day 168) and all other scheduled visits.

The same analysis method as the secondary efficacy analysis in Cohort 3 will be used for all tertiary endpoints except the time to therapeutic effect, as compared between low and high dose SRK-015 arms. The time to therapeutic effect will be assessed using Kaplan-Meier life tables. The following therapeutic effects will be examined separately: improvement of at least 3.0 points from Baseline in HFMSE total score, and improvement of at least 2.0 points from Baseline in RULM score.

3.5 Pharmacokinetic Assessment

3.5.1 Sample Collections for Pharmacokinetic Analysis

SRK-015 concentrations and circulating latent myostatin concentrations will be determined using blood samples collected before and after dosing through the final follow-up visit.

3.5.2 Handling Missing or Below the Lower Limit of Quantification Data

The following general rules will apply for the concentration summary and mean plot construction:

- Below the Limit of Quantitation (BLQ) are set to zero for the calculation of these mean values.
- Missing values are excluded from the calculation of these means.

The following rules will be used to handle BLQ for the PK parameter calculation and individual concentration data:

- If BLQ value(s) occurs in a profile before the first measurable concentration, it is assigned as zero concentration for single dose and as lower limit of quantification (LLOQ) for multiple doses.
- If BLQ values occur between measurable concentrations in a profile, the BLQ should be omitted (set to missing).
- If BLQ values occur after the last measurable concentration in a profile, the BLQ should be omitted (set to missing).
- The BLQ at trough is assigned as LLOQ.

In case of missing predose concentration, the missing component is assumed as zero. For the other missing predose cases, the missing data will not be imputed.

3.5.3 Pharmacokinetic Concentration

Individual plasma concentrations of SRK-015 will be summarized by cohort and dose level at each nominal time point for the PK Population descriptively. Individual plasma concentrations will also be listed for the PK Population. The latent myostatin concentrations will be listed for each patient and summarized by separated cohorts.

Individual plasma concentration will be plotted by cohort and dose level on a linear and semi-log scale against actual sampling time points relative to dosing time. Mean (\pm SD) concentration will be plotted on a linear and semi-logarithmic scale against nominal time points by cohort and dose level, when available. LLOQ will be plotted as a reference line in both instances.

Actual sampling times that are outside the sampling time windows may be excluded from concentration summary and mean concentration plotting but will still be used in the calculations of PK parameters and individual concentration plotting.

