5.2. Secondary Objectives for Both the Treatment Period and Extension Periods

The secondary objectives defined for this study are:

- To characterize the PK of SRK-015
- To evaluate the PD effects of SRK-015
- To evaluate time to therapeutic effect between low- and high-dose SRK-015 in a predefined cohort (Cohort 3)
- To evaluate the immunogenicity of SRK-015
- To evaluate the effect of SRK-015 on quality of life

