9.3. Pharmacodynamics Blood Sample Collection

Blood samples will be collected for the measurement of latent myostatin levels. These blood samples will be obtained prior to infusion as indicated in the schedule of assessments in [Table 2](#), [Table 3](#), [Table 4](#), and [Table 5](#). The 2-hour (+30-minute window) postdose (from stop of infusion) sample collection on Day 0 must be collected via peripheral venipuncture. Each collected sample will be split into approximately equal volume sample sets to allow for retesting, if required. Aliquots from the PD blood samples may be used for biomarker testing (Extension Period C only) or additional PK or immunogenicity testing as appropriate, and Baseline and postbaseline samples may be used to support PK, PD, and/or ADA assay validation.

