11.2. Analysis Strategy

All prespecified safety and efficacy endpoints will be analyzed by cohort and by dose group for Cohort 3. All patients with any postbaseline data will be included in the interim and primary analyses. In addition, safety and efficacy data for the high dose will be analyzed for different cohort/dose combinations taking cohort, dose level, and receiving background SMA therapy into consideration. For the change from Baseline analyses (to utilize the patient as their own control for response analyses), the last observation before the first dose will be used as the Baseline. Cohort 3 low- vs high-dose treatment outcomes will also be evaluated for the time to response as a descriptive outcome.

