11.2.3. Pharmacokinetic and Pharmacodynamic Analysis

All patients who receive at least 1 dose of study drug and have at least 1 quantifiable PK result will be included in the population PK analysis. The data from this study may be combined with other Sponsor SMA studies for both population PK analysis and exposure-response analysis, if data permit. SRK-015 concentrations and circulating latent myostatin concentrations will be determined using blood samples collected before and after dosing through the final follow-up visit. SRK-015 concentrations will be listed and summarized in tabular formats using descriptive statistics and will be plotted against time points by cohort, and dose and schedule. The latent myostatin concentrations will be listed for each patient and summarized by cohort.

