11.2.4. Anti-SRK-015 Antibody Analysis

All patients who receive at least 1 dose of study drug and have at least 1 ADA result will be included in the immunogenicity evaluation. The ADA population is defined as patients who receive at least 1 dose of study drug and have a pretreatment result and at least 1 posttreatment result from the ADA sample collection. Immunogenicity will be evaluated through a 3-tier ADA assay (screening, confirmatory, and titer) and a neutralizing antibody assay. The number and percent of patients who become positive for ADAs and who develop neutralizing antibodies will be listed and summarized in tabular format using descriptive statistics by cohort, visit, dose and schedule, and overall.

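### Latent myostatin is summarised by cohort but not by dose, so the planned Cohort 3 summary pools the randomised 2 and 20 mg/kg arms and leaves the low-dose saturation premise without a prespecified by-dose check

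*Combined protocol and SAP*

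**What the plan says.** Latent myostatin is the only PD analyte that the documents name. Protocol 9.3 states: "Blood samples will be collected for the measurement of latent myostatin levels". Protocol 5.2 makes PD a secondary objective: "To evaluate the PD effects of SRK-015".

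Three places set the rule for reporting the marker:

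- SAP 3.5.3: "The latent myostatin concentrations will be listed for each patient and summarized by separated cohorts".
- SAP 3.5.4 repeats that sentence.
- Protocol 11.2.3: "The latent myostatin concentrations will be listed for each patient and summarized by cohort".

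None of them names dose, visit or change from Baseline. SAP section 6, which lists departures from the protocol's statistical section, is silent on the point.

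Other measures are broken down by dose:

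- Drug concentration, SAP 3.5.3: "Individual plasma concentrations of SRK-015 will be summarized by cohort and dose level at each nominal time point". Its plots are by cohort and dose level as well.
- Safety and efficacy, protocol 11.2: "All prespecified safety and efficacy endpoints will be analyzed by cohort and by dose group for Cohort 3". PD is not mentioned in that rule.
- Antidrug antibodies, protocol 11.2.4: "by cohort, visit, dose and schedule, and overall".

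Protocol 8.3 and SAP 2.2.2 allocate Cohort 3 1:1 to 2 or 20 mg/kg. Cohorts 1 and 2 receive 20 mg/kg only. Protocol 4.7 says of the 2 mg/kg arm: "At this dose level, it is anticipated that target saturation will not be attained upon the first dose and thus would require additional dosing". It describes the 20 mg/kg arm as aimed at rapid saturation that is then sustained.

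**The concern.** In Cohorts 1 and 2 a by-cohort summary is also a by-dose summary, so nothing is lost. In Cohort 3 the two differ, and the rule averages randomised arms that are tenfold apart in dose and are expected to engage the target on different time courses.

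The protocol expects the low dose to fall short of saturation at first. That is the premise behind comparing the arms. If time to effect turns out similar in the two arms, a reader needs the marker by arm to tell two explanations apart: the low dose also saturated the target, or saturation was not needed. If time to effect differs, the marker by arm shows whether target engagement differed too. A pooled summary helps with neither question, and it is an uninformative result for the PD objective in the one cohort where dose was randomised.

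**Working it through.** **The plan's own figure.** The documents give no figure for the PD summary. The nearest is protocol Table 9 (SAP Table 2): 10 patients per group, effect size 1.325, two-sided 5%, 80% power. A two-sample t-test on 18 degrees of freedom (noncentral t) gives 80.0%, so it reproduces. The point does not rest on it; it supplies only the 10 per arm.

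**Which outputs carry dose.**

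| Measure | Cohort named | Dose named | Where |
|---|---|---|---|
| SRK-015 concentration | yes | yes | SAP 3.5.3; protocol 11.2.3 |
| Antidrug antibodies | yes | yes | protocol 11.2.4 |
| Efficacy | yes | yes | protocol 11.2; SAP 3.4 |
| Safety | yes | yes | protocol 11.2; SAP 3.6 |
| Latent myostatin | yes | no | protocol 11.2.3; SAP 3.5.3, 3.5.4 |

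**What pooling does.** Assumed for illustration: the high-dose rise is 100, the low dose reaches a fraction f of it, the within-arm SD is s, and there are 10 patients per arm.

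- Pooled mean = (100f + 100)/2.
- Each arm mean lies d = 50(1 − f) from the pooled mean.
- Pooled SD = √[(18s² + 20d²)/19].

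| f | Pooled mean | Pooled SD, s = 20 | Pooled SD, s = 40 |
|---|---|---|---|
| 0 | 50 | 54.9 | 64.4 |
| 0.25 | 62.5 | 43.1 | 54.7 |
| 0.5 | 75 | 32.2 | 46.6 |
| 0.75 | 87.5 | 23.3 | 41.0 |
| 1 | 100 | 19.5 | 38.9 |

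For f = 0.5 and s = 20: d = 25, and √[(7,200 + 12,500)/19] = 32.2. The same mean of 75 and SD of 32.2 would also arise if both arms averaged 75 with a within-arm SD of 32.2 × √(19/18) = 33.1. Mean and SD together do not separate the two situations.

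**Can low-dose engagement be taken as known?** Protocol 4.7 gives a half-life of 23 to 33 days and a plateau at single doses of 3 mg/kg or more, both in healthy adults. Assume first-order kinetics and 28-day dosing, so r = 2^(−28/half-life) = 0.43 to 0.555.

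- Peak load at the second 2 mg/kg dose: 2(1 + r) = 2.9 to 3.1 mg/kg-equivalent.
- Peak at steady state: 2/(1 − r) = 3.5 to 4.5.
- Trough after the first dose: 2r = 0.9 to 1.1.
- Trough at steady state: 2r/(1 − r) = 1.5 to 2.5.

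These values lie on both sides of 3 mg/kg. The documents do not support treating a single-dose plateau in adults as a body-load threshold for patients on repeat dosing. The calculation therefore shows only that low-dose saturation cannot be presumed either way. It is not a prediction.

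**The case against.** The strongest reply is that only one table is affected.

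- The same sentence plans patient-level listings.
- SAP 5.1.1 has staff who hold the Cohort 3 assignments examine how PK, PD and efficacy relate at the 6-month interim.
- Protocol 11.2.3 allows exposure-response analysis where the data allow it.
- SAP section 7 leaves table shells to separate documents, which may already split the marker by dose.
- The study is descriptive, and protocol 4.7 supports the later change of dose for low-dose patients with HFMSE and safety results, not with the PD summary.

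Most of this stands as a limit on the size of the point. It does not fill the gap. A listing is not a summary. The interim look is shown in aggregate. That wording reads as protection of the blind and neither requires nor excludes a by-dose display. The exposure-response analysis is conditional. Unseen shells cannot be relied on, and the governing text names cohort only. The by-dose plots in SAP 3.5.3 might be thought to include the marker, but that passage speaks of plasma concentration, the term the section uses for SRK-015.

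A reader might also infer that the low-dose arm was added to learn whether 2 mg/kg engages the target. Protocol 4.7 does not say so. It gives the aim as the time course of clinical effect and its relation to drug exposure, and incomplete saturation is the premise. Nor does the secondary objective on time to therapeutic effect need PD data: SAP 3.4.3.3 defines it by a gain of at least 3.0 HFMSE points and, separately, at least 2.0 RULM points. By-dose PD would help to interpret that result, not to produce it.

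**Conclusion.** The point holds as a gap in the prespecified summaries. Read as written, protocol 11.2.3 and SAP 3.5.3 and 3.5.4 pool two randomised arms in the Cohort 3 PD summary, and no other section orders a by-dose PD output. This weakens the secondary PD objective and the interpretation of the dose comparison. No primary or safety conclusion changes, and nothing is lost for good.

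It would go too far to infer that the trial cannot show low-dose target engagement. That is true of the planned summary, not of the data. No figure for how far a pooled mean would sit below plateau should be taken from this either: the documents give no by-dose PD values, and any such figure repeats whatever low-dose response is assumed. That the summary cannot separate the arms needs no such assumption. It rests only on the text and the 1:1 allocation.

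**What to change.** In SAP 3.5.3 and 3.5.4 and protocol 11.2.3, state that latent myostatin will be summarised and plotted by cohort and, within Cohort 3, by randomised dose level at each nominal visit through Day 364, as value and change from Baseline.

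Add a rule for the extension: group by randomised arm and by dose at sampling. Protocol 6.2 and SAP 2.2.1 say that low-dose patients move to 20 mg/kg at varying times, so a plain split by dose after Day 364 would be ambiguous.

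The cost is a sentence in each section and one more grouping variable in the PD tables and plots. Cohort 3 then has two summaries of about 10 patients in place of one of about 20. No new samples are needed, and sample size, power and alpha stay as they are. The 12-month analysis already reports Cohort 3 efficacy by dose, so the assignments are in use there. This is a free improvement.
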